13.5. Sample Size Sensitivity

There was no need to perform sample size sensitivity analysis.

13.5.1. Sample Size Re-estimation

Sample size re-estimation is not planned for this study.

13.6. Data Analysis Considerations

13.6.1. Analysis Populations

All Treated Subjects Population: This will consist of all subjects who received at least one dose of study treatment. Safety and clinical activity data will be evaluated based on this population.

The Pharmacokinetic Population: This will consist of those subjects in All Subjects Population and for whom a PK sample is obtained and analyzed.

The Pharmacodynamic Population: This will consist of those subjects in All Subjects Population and who contribute PD/Biomarker samples.

13.7. Interim Analysis

13.7.1. Part 1: Dose-Escalation

In Part 1, interim analyses to inform dose escalation will be performed following the completion of each monotherapy and combination dose cohort in part 1. The primary driver for dose escalation decisions in Part 1 will be governed by an N-CRM model for the mono-therapy dose cohorts and a Bayesian copula regression for the combination dose cohorts. They will be used to predict the probability of DLT at the dose levels yet to be tested to further guide these decisions. Further details of the model will be provided in the RAP

Interim analysis on Part 1 may also be conducted when all subjects enrolled in in Part 1 have had at least one post-baseline disease assessments or progressed or died or withdrawn from the study.

The goal of the interim analysis will be to further evaluate the RP2D for part 2. The totality of the data will be considered when making this evaluation.

Additionally, safety, PK, PD/biomarker data may be examined during Part 1. Prior to determining GSK2879552 dose for the next monotherapy cohort, exploratory analysis maybe conducted to assess the relationship of GSK2879552 dose levels with safety, PK and PD parameters using all data from available cohorts.

13.7.2. Part 2: Expansion Cohort

After the initial 10 evaluable subjects have enrolled at the RP2D dose, response data will be reviewed on an ongoing basis and the number of responses observed will be compared

with the stopping rules provided in Section 13.4.2. As noted in Section 13.4 data from Part 1 at the RP2D may be combined with data from part 2 to achieve the required number of subjects for the response rate analysis.

13.8. Key Elements of Analysis Plan

Data will be listed and summarized according to the GSK reporting standards, where applicable. Data will be listed and summarized mostly by doses. Separate analyses will be provided for Part I and in Part II where applicable. In some instances, analysis may also be generated based on the dose of GSK2879552. Data from Part I and Part II may be combined for some analyses at the end of the trial, for subjects treated at the same dose level. Complete details will be documented in the Reporting and Analysis Plan (RAP). Any deviations from, or additions to, the original analysis plan described in this protocol will be documented in the RAP and final study report.

As it is anticipated that accrual will be spread thinly across centers and summaries of data by center would be unlikely to be information, data from all participating centers will be pooled prior to analysis.

All data up to the time of study completion/withdrawal from study will be included in the analysis, regardless of duration of treatment.

As the duration of treatment for a given subject will depend on efficacy and tolerability, the duration of follow-up will vary between subjects. Consequently there will be no imputation for missing data.

Demographic and baseline characteristics will be summarized.

13.8.1. Anti-Cancer Activity Analyses

For Part 1, anti-tumor activities will be evaluated based on clinical evidence and response criteria. If the data warrant, the response data will be summarized by dose level.

The primary aim of Part 2 is to detect a clinically meaningful response rate of 30% relative to a 10% response rate suggesting no activity.

Response rate (RR) is defined as the percentage of subjects who achieved CR, CRp, PR or morphologic leukemia-free state (MLFS) among subjects who received at least one dose of treatment. Response rate and the associated 2-sided 95% exact confidence limits will be provided. A waterfall plot of percent change from baseline in bone marrow blasts and peripheral blasts will be provided.

As a secondary analysis, if data warrant, PFS, OS, DOR, and TTR will be evaluated using the Kaplan-Meier method. Summaries of median time to event, quartiles and 95% CIs will be presented.

For the analysis of PFS, if the subject received subsequent anti-cancer therapy prior to the date of documented events, PFS will be censored at the last adequate assessment (e.g. assessment where visit level response is CR, CRp, PR, MLFS, or SD) prior to the

initiation of therapy. Otherwise, if the subject does not have a documented date of events, PFS will be censored at the date of the last adequate assessment. For the analysis of overall survival (OS), the last date of known contact will be used for those subjects who have not died at the time of analysis; such subjects will be considered censored. Further details on rules for censoring will be provided in the RAP. Sensitivity analyses of PFS and further details on censoring rules will be provided in the RAP. Progression free survival (PFS) and overall survival (OS) will be summarized using Kaplan-Meier method.

The duration of response is defined for the subject or subjects with a CR, CRp, MLFS, or PR, as the time from the first documented evidence of a CR, CRp, MLFS, or PR until the first documented disease progression or death due to any cause. Censoring rules for duration of response will be outlined in detail in the RAP.

Time to Response is defined, for subjects with a CR, CRp, MLFS, or PR, as the time from first dose to the first documented evidence of responses (PR or better).

If the data warrant, duration of response and time to response will be summarized descriptively using Kaplan-Meier medians and quartiles. Only the subset of subjects who show a confirmed complete or partial tumor response will be included. Censoring rules for duration of response will follow the rules for PFS outlined in detail in the RAP.

13.8.2. Safety Analyses

The All Treated Subjects Population will be used for the analysis of safety data. All serially collected safety endpoints (e.g. laboratory tests, vital signs, electrocardiogram [ECGs]) will be summarized according to the scheduled, nominal visit at which they were collected and across all on-treatment time points using a “worst-case” analysis. Complete details of the safety analyses will be provided in the Reporting and Analysis Plan (RAP).

Safety endpoints are described in Section 2. Complete details of the safety analyses will be provided in the RAP.

A listing by subject including treatment administered, and compliance, will be generated with dates and times of treatment administered. The number of subjects exposed to study drug will be tabulated for Part 1 (for each dose cohort) and Part 2.

All relevant safety data will be listed and summarized according to IDSL standards. The reporting and analysis plan will list the IDSL templates for the displays. Adverse events will be coded and grouped by system organ class (SOC) and preferred (coded) term (PT) using the Medical Dictionary for Regulatory Activities (MedDRA) system for adverse event coding. AEs will be graded according to the National Cancer Institute Common Terminology Criteria for Adverse Events (NCI CTCAE) Version 4.03. Adverse events will be summarized by maximum toxicity grade for each initial dose level. All AEs will be listed. A summary of the number and percent of subjects reporting each AE at least once will be produced for all AEs, for drug-related AEs and for SAEs for Part 1 (for each dose cohort) and Part 2. A listing of those AEs identified as dose-limiting toxicities will also be produced for each dose cohort for Part 1. A listing showing the relationship of AE

verbatim text to group terms and body systems will also be produced. A listing of withdrawals due to AEs will be provided. Deaths and SAEs will be listed should they occur.

Clinical laboratory evaluations will be performed on the days specified in the Time and Events Table. Clinical chemistry, coagulation, hematology and urinalysis values and change from baseline values will be listed for each subject and flagged high or low relative to their normal ranges, where applicable. The toxicity grade for laboratory data will be calculated using NCI CTCAE Version 4.03. The lab data will then be summarized according to the subject's baseline grade and maximum grade for each cycle of therapy. A listing of subjects with potentially clinically important lab abnormalities will also be produced. A summary of lab values and change from (baseline) may be done for Part 1 (for each dose cohort) and Part 2.

Vital signs and ECG data will be listed and summarized for Part 1 (for each dose cohort) and Part 2. Changes from baseline will be included in the listings and summary.

ECOG Performance Status assessments will be listed and summarized for Part 1 (for each dose cohort) and Part 2.

13.8.3. Pharmacokinetic Analyses

13.8.3.1. Pharmacokinetic Parameters

Pharmacokinetic analysis will be the responsibility of the Clinical Pharmacology Modeling and Simulation (CPMS) Department, GSK.

Non-compartmental Pharmacokinetic Analyses

Pharmacokinetic analysis of GSK2879552 and ATRA, as appropriate, in Part 1 will be conducted by non-compartmental methods. The following pharmacokinetic parameters will be determined if data permit:

- maximum observed plasma concentration (C_{max})
- time to C_{max} (t_{max})
- area under the plasma concentration-time curve ($AUC[0-t]$ and/or $AUC[0-\infty]$) after single dose and $AUC(0-t)$ and $AUC(0-\tau)$ after repeated administration
- apparent terminal phase elimination rate constant (λ_z)
- apparent terminal phase half-life ($t_{1/2}$)

GSK2879552 trough concentration (C_τ) samples collected on the specified days will be used to assess attainment of steady state. To estimate the extent of accumulation for GSK2879552 after repeat dosing, the observed accumulation ratio (R_o) may be determined from the ratio of $AUC(0-\tau)$ in Day 15/ $AUC(0-\tau)$ in Day 1. The ratio of $AUC(0-\tau)$ on Day 15/ Day 1 $AUC(0-\infty)$ will be calculated to assess time invariance for GSK2879552.

GSK2879552 concentrations may be determined in urine samples to determine urinary recovery of unchanged drug and renal clearance.

Metabolic Profiling

In a subset of subjects, plasma samples may be pooled and analyzed qualitatively for circulating metabolites; 0-24 hour urine samples may also be analyzed for GSK2879552 and compound related metabolites. These results will be performed under a separate protocol and reported separately.

Population Pharmacokinetics

Plasma concentration-time data from Part 2 (Expansion Cohort) will be combined with data from Part 1 and possibly with data from other studies and analyzed using a population approach. A nonlinear mixed effects model will be used to determine population PK parameters (absorption rate, K_a , apparent clearance, CL/F and volume of distribution, V/F) and summary exposure measures (C_{max} , AUC and $C_{av} = AUC/\tau$) and identify relevant covariates (e.g., age, weight, or disease related covariates). Results may be reported separately.

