1.3.4. Pharmacokinetics of GSK2879552 in Humans

GSK2879552 pharmacokinetics (PK) will be evaluated in a limited number of subjects in the first time in human study in small cell lung cancer patients (GSK study 200858, NCT# 02034123) prior to the initiation of this study. PK of GSK2879552 in human were predicted using in vitro microsomes and hepatocytes data, as well as in vivo intravenous (IV) pharmacokinetic data from mice, rats, and dogs combined with simple allometric scaling and Dedrick transformation. The human blood clearance is predicted to be around 5.4 mL/min/kg for a 70 kg human. The human blood volume of distribution is predicted to be most likely between 1.0 and 1.5 L/kg leading to a range of terminal half-life of 2.1 to 3.2 hours. Based on the good oral bioavailability in animals and the predicted low human clearance, the oral bioavailability is expected to be around 75% to 100% in humans.

As of 20-NOV-2015, the PK of GSK2879552 was evaluated following administration of single (N=18) and repeated (N=16) oral administration of 0.25 mg to 3 mg of GSK2879552 in subjects with SCLC in Study 200858 and following single (N=11) and repeated (N=8) oral administration of 1 mg to 8 mg in subjects with AML in Study 200200. GSK2879552 pharmacokinetics are characterized by a rapid absorption with

maximum concentration occurring typically within the first hour after dosing. GSK2879552 is eliminated slowly with an average terminal phase half-life of 12 to 38 hours, leading to a moderate average increase in exposure of 72% for AUC at 2 mg daily. Following single and repeated administration of 0.25 mg to 4 mg of GSK2879552, C_{max} and AUC tended to increase in a dose proportional fashion.

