2. OBJECTIVES, ENDPOINTS AND HYPOTHESES

PART 1: Escalation Cohort		
	Objectives	Endpoints
Primary	1. To determine the safety, tolerability, MTD and/or RP2D and regimen of GSK2879552, alone or in combination with ATRA, given orally in adult subjects with AML.	1. AEs, SAEs, dose limiting toxicities, dose reductions or delays, withdrawals due to toxicities and changes in safety parameters (e.g., laboratory values, vital signs, electrocardiograms [ECGs], physical examinations).
Secondary	
1. To characterize the PK of GSK2879552, alone or in combination with ATRA, after single- and repeat-dose oral administration.
 
2. To evaluate clinical response after treatment with GSK2879552, alone or in combination with ATRA.
 
3. To characterize the PK of ATRA in combination with GSK2879552 after single and repeat-dose oral administration
	
1. GSK2879552 PK parameters following single-(Day 1) and repeat-dose (Day 15) administration of GSK2879552, including AUC, C_{max}, t_{max}, t_{1/2} (terminal phase and/or effective half-life), accumulation ratio, and time invariance.
 
2. Objective response rate defined as the percentage of subjects achieving complete remission (CR), partial remission (PR), CRp (as per CR but platelet count <100 x 10⁹/L) and morphologic leukemia-free state per response criteria (Cheson, 2003)
 
3. ATRA PK parameters following single and repeat-dose administration of ATRA and GSK2879552, including AUC, C_{max}, t_{max}, t_{1/2} (terminal phase).

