Bone marrow aspirate/biopsy for disease assessment ^{24, 25}	X ²⁰					X ¹⁸						Wk 4, between Wk 6- 8 ¹⁹ , Wk 12 and then every 12 wks.			
Telephone call for survival status ²⁶														X	
PGX sample (buccal swab)	X														
PK blood sample on bone marrow day ¹⁵						X (bone marrow day)						Wk 4, between Wk 6- 8, Wk 12 and then every 12 wks			
Transfusion Assessment ¹³	X				X		X				X		Every week x 4 (wk 4-7), wk 8, then every 4 wks		

	SCR	First Treatment Phase (28 days)										Continuation Phase	EOT	SFU Q12W
		D 1	D 2	D 4	D 8	D 11	D 15	D 16	D 18	D22	D25			
Adverse Events		continuous												
Con Meds		continuous												
Highest Dose in PK/PD expansion cohort ONLY														
Blood for metabolite evaluation		X ⁹	X ⁹				X ⁹	X ⁹						
Urine for metabolite evaluation		X ^{5, 12}	X ⁵				X ⁵	X ⁵						
Urine for PK		X ^{5, 12}	X ⁵				X ⁵	X ⁵						

1. A blood sample will be collected for PK analysis on D1 at following time points: pre-dose, 0.25, 0.5, 1, 1.5, 2, 3, 4, 6, 8, 10, and 24 hrs post dose. In the combination cohort, a blood sample for ATRA PK analysis will be also collected at the same time points except for the 0.25, 10 and 24 hour sample. Additional samples may be collected at 48 and 72 hrs post dose in subjects not receiving a dose on Days 2 and 3 to better characterize the terminal half-life of GSK2879552, if needed.
2. A blood sample will be collected for PK analysis on D8 at following time points: pre-dose, 0.5, 3 hrs post dose. In the combination cohort, a blood sample for ATRA PK analysis will be also collected at the same time points.
3. A blood sample will be collected for PK analysis on D15 at following time points: pre-dose, 0.25, 0.5, 1, 1.5, 2, 3, 4, 6, 8, 10, and 24 hrs post dose. In the combination cohort, a blood sample for ATRA PK analysis will be also collected at the same time points except for the 0.25, 10 and 24 hour sample.
4. PK blood sample should be taken pre-dose around the same time as CBC. If the dose has been modified since the last PK sample and an unscheduled CBC sample is taken, a PK sample should be obtained together with the first unscheduled CBC sample. PK sample will not be collected beyond week 48.

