##### 9.1.1.2. Derived Pharmacokinetic Parameters

Pharmacokinetic analysis of GSK2879552 will be conducted by noncompartmental methods using WinNonlin (Version 6.3 or higher). However pharmacokinetic analysis of ATRA will not be conducted due to the sample size limitations. The following pharmacokinetic parameters will be determined for if data permit:

Parameter	Parameter Description
AUC(0-t)	Area under the concentration-time curve from time zero to the time of the last quantifiable concentration (C(t)) will be calculated using the linear trapezoidal rule for each incremental trapezoid and the log trapezoidal rule for each decremental trapezoid.
$AUC(0-\tau)$	Area under the concentration-time curve during a dosing interval of duration "tau".
AUC (0-∞)	Area under the concentration-time curve extrapolated to infinity will be calculated as: $AUC = AUC(0-t) + C(t) / \lambda_z$ This will be calculated for Day 1 only
C max	Maximum observed plasma concentration, determined directly from the concentration-time data.
t max	Time to reach C max , determined directly from the concentration-time data.
t 1/2	Apparent terminal half-life will be calculated as: $t_{1/2} = \ln 2 / \lambda_z$
λ z	Apparent terminal phase elimination rate constant
C T	Trough concentration

To estimate the extent of accumulation after repeat dosing, the observed accumulation ratio (Ro) may be determined from the ratio of AUC(0- $\tau$ ) in Day 15/ AUC(0- $\tau$ ) in Day 1. The ratio of AUC(0- $\tau$ ) on Day 15/ Day 1 AUC(0- $\infty$ ) will be calculated to assess time invariance.

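### Half-life is derived only as a terminal value from profiles that mostly end at 24 h, although the endpoint also allows an effective half-life that the planned accumulation ratio already supplies

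*Protocol*

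**What the plan says.** Protocol Section 2 makes half-life part of the first Part 1 secondary endpoint, worded as "terminal phase and/or effective half-life), accumulation ratio, and time invariance". SAP 2.2 repeats it.

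The derivations are narrower. Protocol 13.8.3.1 opens its list with "The following pharmacokinetic parameters will be determined if data permit" and includes only the "apparent terminal phase half-life". SAP 9.1.1.2 does the same ("Apparent terminal half-life will be calculated as" ln2 divided by λz). No SAP table or listing is titled for an effective half-life.

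Routine sampling on Days 1 and 15 (Protocol 7.1, Table 3, footnotes 1 and 3) is "pre-dose, 0.25, 0.5, 1, 1.5, 2, 3, 4, 6, 8, 10, and 24 hrs post dose". Protocol 4.2.4 lets some subjects withhold the Day 2 and Day 3 doses for sampling to 72 h if the half-life exceeds 5 h; footnote 1 makes the 48 and 72 h samples optional. Nothing comparable exists on Day 15.

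Protocol 1.3.4 reports what had been seen in patients: "GSK2879552 is eliminated slowly with an average terminal phase half-life of 12 to 38 hours". It attributes to this a mean rise of 72% in AUC when 2 mg is given every day.

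Protocol 13.8.3.2 and SAP 9.1.3 summarise individual parameters by dose cohort, without separating 24 h from 72 h profiles.

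**The concern.** The protocol predicted a half-life of 2.1 to 3.2 h, for which 24 h of sampling was ample. The observed 12 to 38 h changes that. A terminal slope then rests on a window of two half-lives at best and well under one at worst, with a single sample after 10 h. Of the two quantities the endpoint permits, the plan keeps the one its routine schedule supports least and does not derive the one obtainable from a ratio it already computes.

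Three results are affected. Half-life summaries by dose can mix 24 h and 72 h values that do not estimate the same thing. Day 1 AUC(0-∞) uses the same λz, so a slope read too steep makes that area too small. The time-invariance ratio (SAP 9.1.3.3) and Day 1 dose proportionality (SAP 9.1.3.1) are both built on it; an area that is too small pushes the time-invariance ratio above 1.

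**Working it through.** **1. The plan's own figures.** With one-compartment kinetics and τ = 24 h, Ro = 1/(1 − 2^(−24/t½)). A half-life of 12 h gives 1.33 and 38 h gives 2.82. The stated 72% increase (Ro = 1.72) lies between them and corresponds to an effective half-life of ln2 × 24 / ln(1.72/0.72) = 16.64/0.871 = 19.1 h. The figures are compatible. (SAP 9.1.3.2 gives one as the expected value of Ro; that expectation belongs to the time-invariance ratio, and the protocol's own Ro is 1.72.)

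**2. Window and precision with 24 h sampling.** Share of AUC beyond 24 h = 2^(−24/t½). For a log-linear fit to the 6, 8, 10 and 24 h samples, the mean time is 12 h and the sum of squares is 36 + 16 + 4 + 144 = 200, so relative SE of λz = CV/(λz × √200). At 38 h, λz = 0.0182 and a 10% CV gives 0.10/(0.0182 × 14.14) = 39%. The residual CV of 10% to 20% is an assumption; the documents give none. Percentiles come from 200,000 simulated mono-exponential profiles.

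| True t½ | Window (half-lives) | AUC beyond 24 h | Relative SE of λz, CV 10% / 20% | 5th–95th percentile of estimated t½, CV 10% |
|---|---|---|---|---|
| 12 h | 2.0 | 25% | 12% / 24% | 10.0–15.0 h |
| 19.1 h | 1.26 | 42% | 19% / 39% | 14.5–28.0 h |
| 38 h | 0.63 | 65% | 39% / 77% | 23–103 h |

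At 38 h and CV 20%, about 10% of profiles show no decline at all.

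**3. The same with 48 and 72 h samples.** Fitting 10, 24, 48 and 72 h, relative SE falls to 4–7%, 6–12% and 12–23% at 12, 19.1 and 38 h. The extrapolated share falls to 1.6%, 7% and 27%.

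**4. Bias.** This needs a distribution phase, whose half-life is assumed. Take 65% of AUC in a 38 h phase and the rest in a faster one (Ro is then about 1.72), 15% error, and the best-fitting slope through at least three points:

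- 24 h sampling, Day 1: median about 10, 12 or 20 h for a distribution half-life of 3, 2 or 1 h.
- In the 3 h case, the Day 1 5th–95th percentile range is about 7–15 h; Day 15 gives about 15 h (10–29 h); 72 h sampling gives about 32 h (19–53 h).
- Mono-exponential 19.1 h, 24 h sampling: median 18.5 h, almost unbiased, but ranging from 12.3 to 34.5 h.

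**5. Effective half-life from Ro.** Take Ro = 1.72 and 90% limits Ro × exp(±1.645 σ√(2/n)), with σ² = ln(1 + CV²) and an assumed within-subject AUC CV of 20%. The intervals are 11.7–28.2 h (n = 3), 13.8–25.3 h (n = 6) and 15.2–23.4 h (n = 12). At CV 30% and n = 3 it is 8.4–33.4 h. These use a normal quantile. With the t quantile on 2 degrees of freedom (2.920), n = 3 and CV 20% give a log half-width of 2.920 × 0.198 × 0.816 = 0.472, so Ro runs from 1.07 to 2.76 and effective half-life from 6.2 to 36.9 h.

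**The case against.** Several stronger readings are tempting, and the documents do not support them.

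- *The plan breaches its endpoint.* It does not: the wording is and/or, so terminal half-life alone satisfies it.
- *Sampling is limited to 24 h.* The 72 h option exists and its 5 h trigger is met. It remains discretionary, for some subjects, on Day 1.
- *Every half-life will be biased or very imprecise.* Not near 12 h with mono-exponential decline, and not in the median whenever decline is mono-exponential. The size of the bias depends on a distribution half-life the current text does not give.
- *No acceptance rules exist for λz.* The SAP refers to an internal non-compartmental guideline that is not supplied. One can say only that the SAP text states no minimum span or extrapolation limit.
- *The dosing interval or a washout depends on this estimate.* Protocol 1.4.3.1 rests once-daily dosing on LSD1 protein turnover, and no washout for this drug is derived from its half-life.
- *The 16 h in Protocol 4.8.4.1 contradicts 12 to 38 h.* It lies inside that range; what is missing is a label saying which type of half-life it is.

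It is also fair that effective half-life describes accumulation, does not repair a terminal slope, is undefined when Ro is 1 or less, and is imprecise in small cohorts. The endpoint is secondary and descriptive, parameters are conditional on the data, and the report is abbreviated after early termination. All of this limits the stakes. It does not justify summarising 24 h and 72 h terminal values together or leaving the planned Ro unused.

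**Conclusion.** The point holds as a worthwhile analysis improvement, not as an error in the endpoint. The plan derives only terminal half-life from profiles that routinely cover 0.63 to 2.0 half-lives. Towards the upper end of the stated range the 24 h value is very imprecise (23–103 h for a true 38 h, assumed CV 10%) and, if a distribution phase remains, biased low (medians of about 10 to 20 h on Day 1). Near 12 h with mono-exponential decline it is usable. The arithmetic on window length and on the 25% to 65% of Day 1 AUC extrapolated uses the protocol's own half-lives and assumes mono-exponential decline. The precision and bias figures rest on the assumed error and distribution phase.

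**What to change.** In SAP 9.1.1.2, and in Protocol 13.8.3.1 for consistency:

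- Add effective half-life = ln2 × τ / ln(Ro/(Ro − 1)), with Ro = AUC(0-τ) Day 15 / AUC(0-τ) Day 1, derived only when Ro > 1. Summarise it by dose alongside terminal half-life, preferably by transforming the cohort geometric-mean Ro and its 90% limits from SAP 9.1.3.2. Where the lower limit of Ro is 1 or less, report the lower limit of half-life as not estimable. State that the formula assumes linear, time-invariant kinetics.
- Summarise terminal half-life from profiles with 48 and 72 h samples separately from 24 h-only profiles, and flag the latter as not reliably estimated.
- Report the λz window and the percentage of AUC(0-∞) extrapolated for each profile, so that time invariance and Day 1 dose proportionality can be read with them.
- Do not screen profiles by requiring a span of at least two estimated half-lives. That keeps the profiles biased short: in the 38 h case with a 3 h distribution phase about 30% pass, with a median near 8 h, and at a mono-exponential 19.1 h essentially none pass.

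The cost is one derived variable and a few reporting rules on data already planned. Effective half-life needs both a Day 1 and a Day 15 profile and will be imprecise in small cohorts, and fewer subjects will contribute to the 72 h terminal summary.
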